#### **Risks**

##### Bleeding-Related Events

There have been reports of hemorrhagic events in subjects treated with ibrutinib both with and without thrombocytopenia. These include primarily minor hemorrhagic events such as contusion, epistaxis, and petechiae; and some major hemorrhagic events including gastrointestinal bleeding, intracranial hemorrhage, and hematuria. Use of ibrutinib in subjects requiring other anticoagulants or medications that inhibit platelet function may increase the risk of bleeding. Subjects with congenital bleeding diathesis have not been studied.

##### Atrial Fibrillation

Atrial fibrillation and atrial flutter have been reported in subjects treated with ibrutinib, particularly in subjects with cardiac risk factors, hypertension, acute infections, and a previous history of atrial fibrillation. In particular, subjects with a history of cardiac arrhythmias should be monitored closely. For atrial fibrillation which persists, consider the risks and benefits of ibrutinib treatment and follow the protocol dose modification guidelines.

##### Cytopenias

Treatment-emergent Grade 3 or 4 cytopenias (neutropenia, thrombocytopenia, and anemia) were reported in subjects treated with ibrutinib.

##### Diarrhea

Diarrhea is the most frequently reported nonhematologic AE with ibrutinib monotherapy and combination therapy. Other frequently reported gastrointestinal events include nausea, vomiting, and constipation. These events are rarely severe. Should symptoms be severe or prolonged, ibrutinib treatment should follow the protocol dose modification guidelines.

### Infections

Fatal and non-fatal infections have occurred with ibrutinib therapy. At least 25% of subjects with MCL and 35% of subjects with CLL had Grade 3 or greater infections per NCI Common Terminology Criteria for Adverse Events (CTCAE v4.03). The most commonly reported infections include pneumonia, cellulitis, urinary tract infection and sepsis. Although causality has not been established, cases of progressive multifocal leukoencephalopathy (PML) have occurred in patients treated with ibrutinib.

### Liver Failure

Rare cases of liver failure have been reported in patients treated with ibrutinib.

### Non-Melanoma Skin Cancer

Non-melanoma skin cancers have occurred in patients treated with ibrutinib. Monitor patients for the appearance of non-melanoma skin cancer.

### Rash

Rash has been commonly reported in subjects treated with either single agent ibrutinib or in combination with chemotherapy. In a randomized Phase 3 study (PCYC-1112-CA), rash occurred at a higher rate in the ibrutinib arm than in the control arm. Most rashes were mild to moderate in severity.

### Tumor Lysis Syndrome

There have been reports of tumor lysis syndrome (TLS) events in subjects treated with single-agent ibrutinib or in combination with chemotherapy. Subjects at risk of tumor lysis syndrome are those with comorbidities and/or risk factors such as high tumor burden prior to treatment, increased uric acid (hyperuricemia), elevated lactate dehydrogenase (LDH), bulky disease at baseline, and pre-existing kidney abnormalities.

### Lymphocytosis and Leukostasis

Upon initiation of treatment, a reversible increase in lymphocyte counts (i.e.,  $\geq 50\%$  increase from baseline and an absolute count  $> 5000/\text{mcL}$ ), often associated with reduction of lymphadenopathy, has been observed in most subjects with CLL/SLL treated with ibrutinib. This effect has also been observed in some subjects with MCL treated with ibrutinib. This observed lymphocytosis is a pharmacodynamic effect and should not be considered progressive disease in the absence of other clinical findings. In both disease types, lymphocytosis typically occurs during the first few weeks of ibrutinib therapy (median time 1.1 weeks) and typically resolves within a median of 8.0 weeks in subjects with MCL and 18.7 weeks in subjects with CLL/SLL.

A large increase in the number of circulating lymphocytes (eg,  $> 400000/\text{mcL}$ ) has been observed in some subjects. Lymphocytosis was not observed in subjects with WM treated with ibrutinib. Lymphocytosis appeared to occur in lower incidence and at lesser magnitude in subjects with CLL/SLL receiving ibrutinib in combination with chemoimmunotherapy.

## Interstitial lung disease

Cases of interstitial lung disease (ILD) have been reported in subjects treated with ibrutinib. Randomized, controlled Phase 3 studies did not show an increased incidence rate of ILD in subjects treated with ibrutinib as compared to subjects treated with active control. Subjects should be monitored and evaluated for symptoms (eg, dyspnea, cough or pyrexia) and treated symptomatically, including interruption of the suspected agent as appropriate.

## **3.0 Patient Eligibility**

---

The eligibility criteria listed below are interpreted literally and cannot be waived. An abnormal test (such as a WBC) may be repeated, or a low hemoglobin or platelet count may be corrected with transfusion to make the patient eligible for study. Tests should be performed within 10 days of study entry. (For patients who re-enter the study after receiving autologous or allogeneic transplantation, they will be re-screened for eligibility per the inclusion and exclusion criteria).

### **3.1 Inclusion Criteria**

- Patients must have histologically documented or cytologically confirmed Hodgkin lymphoma with CD30 expression.
- Patients must have ANC  $\geq 1000/\mu\text{L}$ , Plt  $\geq 50,000/\mu\text{L}$ , and hemoglobin  $\geq 8.5 \text{ g/dL}$ . Neupogen can be given before and during treatment to achieve target ANC  $\geq 1000/\mu\text{L}$ . Platelet transfusion and packed red blood cell transfusion can also be given prior to the start of treatment and during treatment to achieve a target plt  $\geq 50,000/\mu\text{L}$  and hemoglobin of  $\geq 8.5/\mu\text{L}$  provided that patients have not received growth factors for at least 14 days prior to entering trial.
- Patients must have measurable disease  $> 1.5 \text{ cm}$  evidenced by CT scan of the neck/chest/abd/pelvis or CT/PET scans.
- Patients must be either refractory to or relapsed after 1 line of therapy.
- Prior radiation therapy is allowed.
- Voluntary written informed consent before performance of any study-related procedure not part of normal medical care, with the understanding that consent may be withdrawn by the subject at any time without prejudice to future medical care.
- Female subject is either post-menopausal, surgically sterilized, or willing to use an acceptable method of birth control (i.e. a hormonal contraceptive, intra-uterine device, diaphragm with spermicide, condom with spermicide, or abstinence) for the duration of the study.
- Male subject agrees to use an acceptable method of contraception for the duration of the study.
- Age  $\geq 15$  years old and over 40 kg. Life expectancy of greater than 3 months.
- ECOG of 0-2.
- Patients must have normal organ and marrow function as defined below:
  - Total bilirubin within 1.5x the upper limit of normal institutional limits. Patients with elevation of unconjugated bilirubin alone, as in Gilbert's disease, are eligible.
  - AST/ALT  $\leq 3.0$ x institutional upper limit of normal (unless demonstrated Hodgkin lymphoma involvement of the liver). Estimated creatinine clearance  $\geq 30 \text{ ml/min}$  (Cockcroft-Gault) and/or 24 urine analysis as needed
  - PT/INR  $< 1.5 \times \text{ULN}$  and PTT (aPTT)  $< 1.5 \times \text{ULN}$ .

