#### 5.1.7 Schedule

For a tabular view of the treatment, monitoring, and follow-up schedule, see study calendar in Section 9

Each cycle is 21 days	Ibrutinib	Brentuximab Vedotin
Dose level 1	420 mg orally daily	1.8 mg/kg IV every 3 weeks
Dose level 2	560 mg orally daily	1.8 mg/kg IV every 3 weeks

Brentuximab vedotin dosing can be given during a window of  $\pm$  3 days due to scheduling issues.

Prior to formally initiating the phase II trial, a *patient safety lead-in* segment will be conducted to ensure there are no unexpected toxicities during cycle 1. Ultimately a total of 39 patients will be treated at phase II and evaluated for response at the ibrutinib/brentuximab vedotin doses considered safe -as determined during the *safety lead-in* segment of this study.

The first nine to twelve patients enrolled will be part of the *patient safety lead-in*. Initially, a group of up to 3 patients can be enrolled on dose level 1; given the potential for overlapping toxicity, the initial dose of ibrutinib tested will be 420 mg daily. During the *safety lead-in*, no more than 3 patients can be under active cycle 1 toxicity evaluation. Note: Unacceptable toxicity in a given patient is defined as any non-hematologic grade 3|4 toxicity or, for hematologic toxicities, any grade 3|4 that does not resolve to a grade 1|2 within 7 days per NCI CTCAE v4.03 toxicity criteria and is considered at least possibly related to ibrutinib and/or brentuximab vedotin, or any other regimen-related cause of death.

The *safety lead-in* segment will follow standard 3+3 dose escalation/de-escalation/expansion rules based on observed toxicity during cycle 1: (Note: Dose de-escalation, escalation or cohort expansion will only take place after 3 patients are fully assessed using the Common Terminology Criteria for Adverse Events (CTCAE) of the National Cancer Institute (NCI) version 4.03 following the completion of cycle 1.)

- If 0 out of 3 evaluable patients experience unacceptable toxicity during cycle 1, then the next dose level of combination therapy will be tested.
- If 1 out of 3 evaluable patients experience unacceptable toxicity during cycle 1, three additional patients will be assessed at the same dose level of combination therapy.

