## 5.5 Supportive Care, Other Concomitant Therapy, Prohibited Medications

Use of neutrophil growth factors or biosimilars is permitted per institutional policy and the American Society of Clinical Oncology (ASCO) guidelines. Transfusions may be given in accordance with institutional policy.

Any medications known to cause QT prolongation should be used with caution; periodic ECG and electrolyte monitoring should be considered.

Warfarin or vitamin K antagonists should not be administered concomitantly with ibrutinib. Supplements such as fish oil and vitamin E preparations should be avoided. Use ibrutinib with caution in subjects requiring other anticoagulants or medications that inhibit platelet function. Subjects with congenital bleeding diathesis have not been studied. For subjects requiring the initiation of therapeutic anticoagulation therapy (e.g. atrial fibrillation), consider the risks and benefits of continuing ibrutinib treatment. If therapeutic anticoagulation is clinically indicated, treatment with ibrutinib should be held and not be restarted until the subject is clinically stable and has no signs of bleeding. Subjects should be observed closely for signs and symptoms of bleeding. No dose reduction is required when study drug is restarted.

Chemotherapy, anticancer immunotherapy, corticosteroids for cancer-related reasons (at doses equivalent to prednisone >20 mg/day for >14 days), experimental anticancer therapy, or radiotherapy are prohibited while the subject is receiving ibrutinib and brentuximab vedotin. Corticosteroids for the treatment of non-cancer-related reasons for longer than 14 days and/or at doses >100 mg/day of prednisone or its equivalent are also prohibited.

Ibrutinib may increase the risk of bleeding with invasive procedures or surgery. The following guidance should be applied during the perioperative period for subjects who require surgical intervention or an invasive procedure while receiving ibrutinib:

For any surgery or invasive procedure requiring sutures or staples for closure, ibrutinib should be held at least 7 days prior to the intervention and should be held at least 7 days after the procedure and restarted at the discretion of the investigator when the surgical site is reasonably healed without serosanguineous drainage or the need for drainage tubes.

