**Brentuximab vedotin (commercial supply):**

**Peripheral Neuropathy:** Peripheral neuropathy should be managed using a combination of dose delay and reduction to 1.2 mg/kg. For new or worsening Grade 2 or 3 neuropathy, dosing should be held until neuropathy improves to Grade 1 or baseline and then restarted at 1.2 mg/kg. For Grade 4 peripheral neuropathy, BV should be discontinued.

**Neutropenia:** Neutropenia should be managed by dose delays and reductions. For grade 1 or 2, continue at same dose. The dose of BV should be held for Grade 3 or 4 neutropenia until resolution to baseline or Grade 2 or lower. Growth factor support should be considered for subsequent cycles in patients who experience Grade 3 or 4 neutropenia. In patients with recurrent Grade 4 neutropenia despite the use of growth factors, and despite dose reduction specified for ibrutinib, discontinuation or dose reduction of BV to 1.2 mg/kg may be considered.

**Anemia and thrombocytopenia:** For Grade 1 or 2, continue at same dose. For Grade 3 and 4, withhold dose until toxicity is  $\leq$  Grade 2 or has returned to baseline, then resume treatment at the same dose level. For second occurrence of Grade 4, withhold until toxicity  $\leq$  Grade 1 or has returned to baseline, then resume treatment at 1.8 mg/kg but reduce ibrutinib dose from 560 mg to 420 mg. For third occurrence, withhold until toxicity  $\leq$  grade 1 or has returned to baseline, then resume BV at 1.8 mg/kg but reduce ibrutinib dose from 420 mg to 280 mg. In patients with recurrent grade 4 anemia and thrombocytopenia despite dose reduction specified for ibrutinib, then resume treatment of BV at 1.2 mg/kg. If patient was already at 1.2 mg/kg of BV, then discontinue treatment of BV and ibrutinib.

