### 10.2 Transplant Endpoint Definitions

**Overall Survival (OS):** OS is defined as the duration of time from start of HCT treatment to time of death (due to any cause). Evaluated and recorded at day 30, day 100, 6 months, 1-year and 2-years post HCT.

**Progression-Free Survival (PFS):** PFS is defined as the duration of time from start of HCT treatment to time of progression or death, whichever occurs first. Evaluated and recorded at day 30, day 100, 6 months, 1-year and 2-years post HCT.

**Relapse/Progression (CIR):** The event is relapse/progression. The time to this event is measured from start of HCT treatment. Deaths without relapse/progression are considered a competing risk. Surviving patients with no history of relapse/progression are censored at time of last follow-up. Evaluated and recorded at day 30, day 100, 6 months, 1-year and 2-years post HCT.

**Non-relapse mortality (NRM):** NRM is defined as death occurring in a patient from causes other than relapse or progression. NRM is measured from start of treatment until non-disease related death, or last follow-up, whichever comes first. Deaths from relapse/progression are considered a competing risk. Evaluated and recorded at day 30, day 100, 6 months, 1-year and 2-years post HCT.

**Stem cell mobilization:** mobilization regimen used, median number of cells collected, median number of days to reach minimum collection.

**Engraftment (Recovery of Granulopoiesis and Megakaryopoiesis):** Engraftment will be assessed using three distinct milestones: 1) (Autologous and Allogeneic) ANC (neutrophils)  $\geq 0.5 \times 10^3/\mu\text{L}$  achieved and sustained for 3 consecutive lab values on different days with no subsequent decline; 2) (Autologous) Platelets (PLT)  $\geq 20 \text{ K}/\mu\text{L}$  independent of platelet transfusion support; and 3) (Allogeneic) PLT  $\geq 25 \text{ K}/\mu\text{L}$

independent of platelet transfusion support. For platelet recovery, date should reflect no transfusions in previous 3 days and the first of 3 consecutive lab values on different days.

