### 11.3 Safety Analysis and Stopping Rules for Excessive Toxicity

Following the *patient safety lead-in segment*, the early stopping rule for safety/toxicity will continue to be assessed for each patient after cycle 1. The expected rate of unacceptable toxicity should not be  $\geq 33\%$ . See section 5.1.7 for unacceptable toxicity definition. This rule is in addition to the quarterly review of all toxicities submitted to the COH DSMC. Given the number of patients treated, if the unacceptable toxicity rate is  $\geq 33\%$ , patient accrual will be halted and a full review of the data by the Data Safety Monitoring Committee (DSMC) will be mandated.

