##### 13.1.4.1 *Major Hemorrhage*

Major hemorrhage is defined as any of the following:

- Any treatment-emergent hemorrhagic adverse events of Grade 3 or higher\*. Any treatment-emergent serious adverse events of bleeding of any grade
- Any treatment-emergent central nervous system hemorrhage/hematoma of any grade

\*All hemorrhagic events requiring transfusion of red blood cells should be reported as grade 3 or higher AE per CTCAE v4.03.

Events meeting the definition of major hemorrhage will be captured as an event of special interest according to Section 13.1.4 above.

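### A transfused platelet or hemoglobin count can close a grade 3|4 cytopenia in lead-in cycle 1, because the 7-day resolution rule does not require an unsupported value

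*Combined protocol and SAP*

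**What the plan says.** **Support allowed.** Section 3.1 permits growth factor ("Neupogen can be given before and during treatment to achieve target ANC") and blood products ("Platelet transfusion and packed red blood cell transfusion can also be given prior to the start of treatment and during treatment"). The stated targets are ANC 1000/µL, platelets 50,000/µL and hemoglobin 8.5. Section 5.5 says of growth factor: "Use of neutrophil growth factors or biosimilars is permitted per institutional policy". It leaves transfusion to institutional policy. The only time limit is on growth factor, in the 14 days before entry. Neither section sets the lead-in apart.

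**Toxicity definition.** The synopsis (Endpoints), 5.1.7 and 11.1.2 carry the same definition. A related non-hematologic grade 3|4 event always counts. A blood-count event counts under this condition: "for hematologic toxicities, any grade 3|4 that does not resolve to a grade 1|2 within 7 days". The definition does not mention supported counts.

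**Use of the definition.** Under 5.1.7 and 11.1.2, the highest dose level with at most 1 of 6 evaluable patients affected in cycle 1 goes to phase II. Two or more of 6 at 560 mg falls back to 420 mg, and two or more of 6 at 420 mg stops the trial. Section 11.3 halts accrual if the unacceptable toxicity rate is 33% or more, and borrows the definition: "See section 5.1.7 for unacceptable toxicity definition".

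**Care taken elsewhere.** For post-transplant engraftment, 10.2 states: "For platelet recovery, date should reflect no transfusions in previous 3 days and the first of 3 consecutive lab values on different days".

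**The concern.** Two stated rules interact. One lets sites raise platelets and hemoglobin with blood products during cycle 1. The other removes a cytopenia from the toxicity count once the value reads grade 1|2 within a week. A post-transfusion value partly measures the transfused product, not recovery from the study drugs. The text nevertheless accepts it as resolution.

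The error runs one way, toward declaring a dose safe. Low platelets are also a foreseeable event here. The one dose-limiting toxicity reported for brentuximab vedotin at 1.8 mg/kg was grade 4 thrombocytopenia (2.1), and thrombocytopenia is on the list of frequent grade 3 or 4 events with ibrutinib combinations (2.4.2). With 3 to 6 patients per dose level, one reclassified patient can change the action. Four sites could also score the same transfused patient differently.

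**Working it through.** **Is there a correcting rule?**

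- 6.2 on neutropenia: "Growth factor support should be considered for subsequent cycles in patients who experience Grade 3 or 4 neutropenia". This is advice about growth factor in later cycles and does not address transfusion.
- 9.0 lists one CBC per week in cycle 1. That is a minimum, but one value may decide a 7-day window.
- 15.3 and 15.6 provide for team and DSMC review but give no rule for scoring a supported count.
- 10.2 requires a transfusion-free platelet count, for engraftment only.

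No section closes the gap.

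**The plan's own figure.** The stated sample size is the Simon design (19 + 20 = 39; boundaries 6/19 and 16/39; 30% against 50%). It reproduces, with exact type I error 0.0455 and power 0.804. It does not depend on this point. The plan states no operating characteristic for the lead-in.

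**Inputs for the size.**

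- Six patients at the declared dose: from the rule of at most 1 in 6, and consistent with the expected lead-in of 9 (3 + 6).
- *a*, non-hematologic unacceptable toxicity: 10% to 15% (assumed).
- *h*, slow-recovering grade 3|4 low platelets or hemoglobin in cycle 1: 1% to 6% (assumed). The upper end is scaled to the 6% of patients with platelet shifts to grade 3 or higher in the single-agent brentuximab vedotin phase 2 studies (2.4.1).
- *m*, the share of those cytopenias closed by a transfused count: 0, one half or all (assumed).

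**Formulas.** With *a* and *h* independent, the scored rate is p = 1 − (1 − a)(1 − h(1 − m)). The chance that the dose passes is P(≤1 of 6) = (1 − p)^6 + 6p(1 − p)^5.

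Example with a = 0.15, h = 0.06, m = 0: p = 1 − 0.85 × 0.94 = 0.201, and P = 0.799^6 + 6 × 0.201 × 0.799^5 = 0.260 + 0.393 = 0.653.

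| a | h | None hidden | Half hidden | All hidden | Rise, half | Rise, all |
|---|---|---|---|---|---|---|
| 0.10 | 0.01 | 0.868 | 0.877 | 0.886 | 0.009 | 0.018 |
| 0.10 | 0.06 | 0.767 | 0.829 | 0.886 | 0.062 | 0.119 |
| 0.15 | 0.01 | 0.756 | 0.767 | 0.776 | 0.010 | 0.020 |
| 0.15 | 0.06 | 0.653 | 0.715 | 0.776 | 0.063 | 0.124 |

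Rises are taken before rounding. They run from about 1 to 6 percentage points with half hidden, and from about 2 to 12 with all hidden.

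**The case against.** **The lead-in should mirror phase II care.** Transfusion is allowed in phase II, so scoring tolerability under the same support is a legitimate choice. That is fair as a principle. The plan does not state that choice, however, and a time-to-recovery rule means little if a transfusion counts as recovery. A sponsor who wants supported counts accepted should say so.

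**Serious consequences are caught anyway.** Related non-hematologic grade 3|4 events count with no 7-day allowance, and for bleeding: "All hemorrhagic events requiring transfusion of red blood cells should be reported as grade 3 or higher AE per CTCAE v4.03". This stands. What can be hidden is mainly a laboratory value without clinical consequence, which is a main reason why the point is minor.

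**The engraftment rule serves another purpose.** In 10.2, independent marrow function is itself the endpoint. That is true, so the comparison does not prove an error. It does show that the protocol already works with a 3-day transfusion-free interval.

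**A stronger reading is tempting.** A reader might infer that growth factor hides neutropenia in the same way, that prophylactic growth factor should be barred in cycle 1, and that the effect is large. Taking 20% slow-recovering cytopenia of every kind, all hidden, with a = 0.10, the chance of passing goes from 0.464 to 0.886, or 42 points. The documents do not support this. The 20% matches the 13% + 7% grade 3 and 4 neutropenia in 2.4.1, which covers all cycles and any duration, and 2.4.1 describes those events as typically short. The growth factor text reads as reactive: 3.1 ties it to reaching a target ANC, 5.5 to institutional policy and ASCO guidelines, and 6.2 to cycles after an event. No section calls for primary prophylaxis, and scoring treated neutropenia as measured is defensible.

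**Conclusion.** The gap is real but minor. Section 3.1 and section 5.5 allow transfusion in lead-in cycle 1, and the unacceptable-toxicity definition accepts any grade 1|2 count within 7 days. Followed literally, a transfused platelet or hemoglobin value removes the event from the rule of at most 1 in 6 and, by reference, from the 33% rule in 11.3.

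The bias favours the higher dose. Its size, about 1 to 6 points with half hidden and 2 to 12 with all hidden, rests on assumed rates, assumed hiding shares and independence of the two kinds of toxicity. The 6% behind the upper end is a single-agent figure over all cycles. The combination could be higher, and slow recovery within cycle 1 alone could be lower. The finding does not extend to growth-factor-treated neutropenia, and it gives no reason to restrict transfusion for patient care.

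**What to change.** Add to the definition in the synopsis (Endpoints), 5.1.7 and 11.1.2:

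*For low platelets or hemoglobin, resolution to grade 1|2 must be shown by a count with no transfusion of that product in the previous 3 days; otherwise the event is unresolved.*

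Section 11.3 then inherits the change through its cross-reference to 5.1.7. List any growth factor given in cycle 1 for the cohort review, with no ban and no patient replacement.

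The cost is one sentence in three places and possibly one extra CBC in a transfused patient. The chance of expanding a cohort or falling back to 420 mg becomes slightly higher. Sample size and the Simon boundaries stay as they are.
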